How does task loading in a PICU environment impact on clinician situational awareness and awareness of the passage of time?

NCT number: ID not yet assigned

Date: 1 Dec 2021

STUDY INVESTIGATORS

- Principal Investigator (A): [name]
 - Email: [contact]
- Principal Investigator (B): [name]
 - Email: [contact]
- Principal Investigator (C): [name]
 - Email: [contact]

1. PICU, Great Ormond Street Hospital, London, UK
2. Attention & Cognitive Control Group, University College London

INTRODUCTION

There is little published literature on the subject of clinician perception of trends in patient observations on PICUs (Paediatric Intensive Care Units) and how this situational awareness is impacted on by clinical tasks. Human factors training cautions against the loss of situational awareness and time perception but there is no supporting observational data in the IC (Paediatric Intensive Care) setting.

Perceptual loading theory hypothesises that, under low load situations, awareness extends to environmental features not directly related to the task at hand. However in high load situations awareness is restricted to the object of focused attention. Individuals experience different load from a given task depending on their skills and experience.

Our pilot project intends to examine how clinician perception is affected by task loading. In our protocol two tasks are undertaken. The administrative task involves requesting a list of investigations from a clinical guideline. The technical task is the uncomplicated insertion of a central venous catheter (CVC) into a simulated vein. In each case we will record proxies for perception: awareness of the passage of time, the time point at which monitoring changes are noted and retrospective recall of observation trends. Our protocol was designed with psychology input from [name], group leader of the UCL Attention & Cognitive Control laboratory.

Passage of time is measured by the participant pressing a foot pedal linked to timing software at every perceived 10 second interval of elapsed time. A retrospective estimate of total elapsed time will also be recorded. After the second task, immediate verbal questions are asked followed by a written questionnaire which contains questions targeting the participant's awareness of monitoring changes.

Analysis will involve paired t testing of the timing interval and observation trend data to see if task loading significantly impacts accuracy.

BACKGROUND

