Participants will be recruited through convenience sampling of those working or training on the ICUs on days when it is possible to run the tasks. Individuals will not be recruited more than once.

Each participant will be given a numeric study ID and parameters recorded against this including:

- Job title- Consultant/fellow
- Gender- Male/female/prefer not to say
- Age- 21-30/31-40/41-50/51-60/61+
- Number of CVCs that they have previously inserted - <10, 10-50, >50).
- Time since last simulation training- 1 week/ 2-4 weeks/ 1-2 months / 3-6 months / 7-12 months / 1-2 years / >3 years

STUDY OUTCOMES

Primary Outcomes

Mean and standard deviation (accuracy) of time intervals measured.

Accuracy of retrospective recall of trends in monitored observations.

Secondary Outcomes

Impact of experience on time perception and monitoring changes.

STUDY PROCEDURES

Recruitment of participants

Participants will be provided with the information sheet appended and given the opportunity to ask any questions before consenting to the study. They will be asked to sign the appended consent form. Their consent forms will be in no way linked to the data collected such that participants could be identified from their data.

Randomisation

Block randomisation will be used to ensure even distribution of individuals at each grade of experience between the allocation groups. A block size of 4 will be used with 2 strata (grade= Consultant, Other). The randomisation list was determined by an online randomisation service ^[27]. The list generated is included as an appendix.

Two parts of the experimental process are randomised.

The first is the order in which the administrative and technical tasks are performed- this is randomised to remove the impact of primacy-recency impacts as well as task training through more practice with the timing apparatus.

The second is the scenario displayed on the monitor. As we are asking participants to identify a trend, randomisation to an increasing or decreasing trend reduces the likelihood of guessing the correct answer.

The study cannot be blinded at the time of data capture given the significant obvious differences between the tasks.

Study procedure

Structure

The overall structure is outlined below with further detail on each section provided in the following section.

Section order	Comment
Consent and discussion	To ensure valid consent and answer queries

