Randomisation	Randomisation of task order and monitor trend scenario: increasing/decreasing
Timing control task	To assess baseline time perception for each participant
Break	To reset and brief the participant for the first task
First task	Administrative or technical task depending on randomisation

Monitor scenario in first task	The parameters do not change aside from a brief desaturation at 30 seconds into the task, to orient participants to the monitor within the task
Break	To reset and brief the participant for the second task
Second task	Administrative or technical task depending on randomisation
Monitor scenario in second task	There is a desaturation at 30 seconds as before to orient participants to the monitor within the task. The blood pressure then either falls or rises, depending on the randomisation, settling at the final value at 4 minutes. The change in blood pressure only occurs in the second task so as to allow immediate review of trend awareness, this is not possible to do after the first task without introducing bias in the second task.
Post task review	To check immediate recall of monitor trends in the second task. Asked immediately to reduce the impact of recall/memory bias on the answers.
Questionnaire	Provides quantification of any trend in parameters noticed.
Debrief	To answer queries and identify any areas of participant support required.

Experimental scenarios:

Each participant will undertake the timing control task first and then both the administrative and technical tasks, the order of these determined by the randomisation table.

1. Timing control

The participant sits and is asked to push a foot pedal every 10 seconds with no reference to external timekeeping. This task continues for 6 minutes.

Participants are instructed: "Please press the foot pedal every 10 seconds, trying to be as accurate as possible. The task will last for several minutes."

After 6 minutes the participant will be asked for the time period they believe has elapsed between the first pedal press and the last.

2. Administrative task:

Request investigations for a new admission

Equipment required:

- PIMS-TS investigations pack
- Computer signed in to the EPIC learning environment for a dummy patient
- Simulated bedside monitor
 - Varies observations over time in line with preset programming determined by the study team
- Foot pedal and data recorder for time logging

Setup

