You have been asked to insert a femoral CVC and have already prepared your equipment.. The line is not flushed. You are already wearing the appropriate sterile gown. Please only use steristrips and dressings, with no sutures, to secure the line to the mannequin. Please document the procedure on the paper provided when you have completed insertion of the line.

I am the nurse in the next bedspace, if at any point you want to make a clinical intervention please continue with the task and verbalise anything you would like me to do.

As before, from when I ask you to begin, please press the foot pedal every 10 seconds, trying to be as accurate as possible. The task will last for several minutes.

Given that this is a simulated mannequin please take all the time you need to familiarise yourself with the ultrasound appearance of the vessels before telling me you are ready to begin.

Events during the task:

Same as for the administrative task.

End point

6 minutes or completion of task documentation.

At the end of the task, progress through the checkpoints below will be noted by the experimenter:

1. Equipment preparation / line flushing
2. Cleaning of the procedure site
3. Initial ultrasound scan
4. Needle manipulation
5. Guide wire insertion
6. Tract dilation
7. Line insertion
8. Line suturing
9. Line dressing
10. Documentation completed

The participant will be asked for the time period they believe has elapsed between the first pedal press and the last.

Post- task review

Following completion of the second task the participant will immediately be asked the following questions:

“Did you see anything of note on the monitor aside from the desaturation” - their yes/no answer is recorded.

“If there were changes in the blood pressure did you notice a fall or a rise” - their rise/fall answer is recorded.

Was the extent of the fall/rise in systolic pressure: 5, 10,15, 20 or 25 mmHg- their selection is recorded.

Which of the tasks did you find more challenging? And why?

They are then asked to describe their subjective experience- “how were those tasks for you?”

They are then asked- “How would you describe your familiarity with EPIC order requesting?”- Very, somewhat, limited, none

They are then provided with the questionnaire from the appendix.

Measurement tools used

- For each experimental run there are 2 variables
 - The task order- administrative or technical completed first

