 - The trend in monitored observations- increasing or decreasing blood pressure in the second task

The following parameters are measured during both tasks:

- Timestamps of foot pedal use by the participant
- Retrospective recall of total elapsed time
- Time to complete task/progress at experiment end
- Question responses

Following completion of the tasks the data collected can be analysed as below.

Time interval analysis:

- Intervals between pedal presses are extracted for each scenario (timing control/administrative/technical tasks)
 - Derive: min/max/mean/interquartile range/standard deviation for each case
- Comparison of the individual’s retrospective perceived elapsed time with actual elapsed time. Reported as percentage error of actual elapsed time.

This will allow the following results to be reported:

- Mean deviation for each individual from their baseline in each of the tasks.
- Change in retrospective perceived elapsed time compared to actual elapsed time.
- Distribution of timing in the control task for each individual.
- Paired t-test comparison to test if there are significant differences in time interval distribution for each individual between control, administrative and technical tasks.
- Overall proportion of participants showing significant deviation from their own baseline in each of the administrative and technical tasks
- Population limits/mean
- Comparison of the mean perceived time interval between subgroups
 - By task order

- By time within task (split into thirds- 2 minutes each)
- By grade
- By number of CVCs previously inserted
- By first 25% vs last 25% of participants

Monitor trend perception analysis:

Each participant will provide question answers from immediately after the second task.

This will allow the following results to be reported:

- Rationale
 - The first question “Did you see anything of note on the monitor” is chosen to highlight inattentive blindness and is asked immediately to avoid any impact from the role of memory or priming from other questions asked.
 - This will be reported as proportion who noted a change
 - The subsequent questions are asked to elicit responses from those who observed the trend but are not sufficiently confident in their recall to report it.
- From the responses the following can be derived:
 - Correct identification of the blood pressure trend- reported as proportion of participants correct

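### The primary timing outcome uses only gaps between pedal presses, so permanent stopping or a late start leaves no trace in it; separately, the recall measure has no defined reference duration

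*Combined protocol and SAP*

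**What the plan says.** The Primary Outcomes list gives the timing outcome as "Mean and standard deviation (accuracy) of time intervals measured". The Time interval analysis section says what those intervals are: "Intervals between pedal presses are extracted for each scenario (timing control/administrative/technical tasks". The statistics to be produced are "Derive: min/max/mean/interquartile range/standard deviation for each case". No press count, omission rate, time to first press or time from last press to task end is listed.

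The period over which participants are asked to press is wider. The technical task instructions say "As before, from when I ask you to begin, please press the foot pedal every 10 seconds, trying to be as accurate as possible", and the administrative instructions are equivalent. Each of these tasks ends at 6 minutes or on completion.

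Recall of duration is asked over a narrower window. For the timing control: "After 6 minutes the participant will be asked for the time period they believe has elapsed between the first pedal press and the last". For the administrative and technical tasks: "The participant will be asked for the time period they believe has elapsed between the first pedal press and the last". The Introduction and the list of measured parameters nevertheless describe this as an estimate of total elapsed time. The analysis compares "retrospective perceived elapsed time with actual elapsed time. Reported as percentage error of actual elapsed time", and nowhere says whether actual elapsed time means the span between presses or the length of the task.

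**The concern.** The period in which participants are told to press and the period that is scored are not the same. A lapse in mid-task lengthens a recorded interval and is counted. A lapse that lasts until the task ends produces no interval, so it drops out of the outcome. The same holds for a delay before the first press.

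This matters because the study looks for impaired time awareness under load. The Background offers reduced capacity to respond to timing queries as one possible explanation of how load affects prospective timing. Giving up the pedal during line insertion is therefore a foreseeable way for the effect to appear. If it happens more often in the technical task, that task loses its longest gaps and the contrast under H_A shrinks. The Outcomes and Significance section says the results may inform procedure guidelines and staffing, so a falsely reassuring result would have consequences.

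The recall measure has a different problem. The window in the question and the reference for the score may not be the same, so one answer can receive two very different errors.

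**Working it through.** **Inputs from the documents.** Target interval 10 s ("Passage of time is measured by the participant pressing a foot pedal linked to timing software at every perceived 10 second interval of elapsed time"); maximum task length 6 min = 360 s; outcome = mean and SD of press-to-press gaps. The plan gives no figure to reproduce here: as a pilot it has no power calculation.

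**Assumption.** The press patterns below are illustrative. The documents give no data on how often participants stop. Pressing is taken as exact up to the stop, to isolate what the outcome can and cannot see.

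**Interval measure.** Presses fall at 10, 20, …, s seconds and then cease. Number of presses = s/10; gaps = s/10 − 1, each 10 s. Expected presses = 360/10 = 36.

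| Last press | Presses of 36 | Planned mean (SD) | Closing gap, 360 − s | Task time per press |
|---|---|---|---|---|
| 360 s | 36 | 10.0 s (0) | 0 s | 360/36 = 10 s |
| 300 s | 30 | 10.0 s (0) | 60 s | 360/30 = 12 s |
| 240 s | 24 | 10.0 s (0) | 120 s | 360/24 = 15 s |
| 180 s | 18 | 10.0 s (0) | 180 s | 360/18 = 20 s |
| 120 s | 12 | 10.0 s (0) | 240 s | 360/12 = 30 s |
| 60 s | 6 | 10.0 s (0) | 300 s | 360/6 = 60 s |

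The planned statistics are identical in every row. To show how much is left out in the 180 s case: adding the closing gap to the 17 recorded gaps gives (170 + 180)/18 = 19.4 s with SD 40.1 s.

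**Late start.** First press at 130 s, then every 10 s to 360 s: 24 presses, 23 gaps, mean 10.0 s, SD 0. This too is invisible.

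**Pause and resume.** Presses to 120 s, none until 250 s, then every 10 s to 360 s: 22 gaps of 10 s and one of 130 s. Mean = (220 + 130)/23 = 15.2 s, SD 25.0 s, maximum 130 s. The planned statistics do capture this.

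**Two-minute thirds.** A stop at 120 s gives 12, 0 and 0 presses in the three thirds. The plan has no rule for a third without presses, so the second and third would be missing values, not errors.

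**Recall measure.** Error = (answer − reference)/reference. For a stop at 120 s, the first-to-last span is 120 − 10 = 110 s.

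| Answer | Reference 110 s (press span) | Reference 360 s (task length) |
|---|---|---|
| 110 s | 0% | (110 − 360)/360 = −69.4% |
| 360 s | (360 − 110)/110 = +227.3% | 0% |

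For a stop at 240 s (span 230 s), the corresponding disagreements are −36.1% and +56.5%. With full compliance from 10 s to 360 s the span is 350 s, and a correct answer about the span is off by only 10/360 = 2.8% against task length. The mismatch is therefore small for compliant participants and large for those who stop early.

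**The case against.** Several objections have force.

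A reader might infer that both timing measures score a participant who stops as accurate. The documents do not support that. It is shown only for the interval measure. The recall score depends on the answer given and on a reference that is not defined, and may come out as no error or a very large one.

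A reader might also infer that the most severe loss of time awareness goes unmeasured. That is too broad. Any lapse followed by one more press enters the mean, SD and maximum, and so does any lengthening of intervals before a stop. Only permanent stopping and a late start are lost.

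The Background passage is tentative and gives two alternatives: less capacity to respond, or less capacity to consult an internal timer. An abandoned pedal may reflect busy hands or feet and not a lost sense of time. This stands, and is a reason to report omission separately from the intervals.

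Most of the raw data are already planned: press timestamps, and completion time or progress at the end. Press counts follow directly, and an analysis by thirds implies a known task start. The gap is thus mainly in the derived endpoint, although no logged start time on the pedal clock is listed.

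Finally, this is a hypothesis-generating pilot. That excuses low power. It does not excuse an endpoint that cannot register one foreseeable form of the effect, and a pilot is the cheapest stage at which to correct it.

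**Conclusion.** The point holds in limited form. By construction, the interval outcome cannot tell a participant who presses accurately and then stops for good, or who starts late, from one who complies throughout. Under the exact-pressing assumption, a stop anywhere from 60 s to 300 s leaves the mean at 10.0 s and the SD at 0, while 30 to 6 of the 36 expected presses are missing. No other planned analysis scores this as error.

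Bias towards no difference under H_A is conditional: permanent stopping would have to be commoner in the technical task. Neither its frequency nor its distribution between tasks is known, so the size of any bias in the trial's result cannot be stated.

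The undefined recall reference is a separate defect and does not depend on anyone stopping, although it matters most when they do. It should be settled before the data are analysed.

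**What to change.** **Timing intervals**
- Log task start and task end on the same clock as the pedal, in all three scenarios.
- Keep the press-to-press mean and SD as planned. Beside them, for each run, report presses made against presses expected (task duration/10 s), or task time per press.
- Report the gap from last press to task end as a separate, right-censored omission measure. Do not average it into the intervals.
- Compare these measures between tasks within participant.
- Count a two-minute third without presses as omitted presses, not as missing data.
- Do not add the gap from start to first press as an interval unless the instructions fix when the first press is due. At present a perfect participant may press at the start signal: presses at 0, 10, …, 360 s would gain a 0 s interval, giving mean 360/37 = 9.73 s and SD 1.64 s instead of 10 s and 0. The same ambiguity moves the press count by one (37 against 36), which is negligible here.

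**Recall**
- Ask for the time from the start signal to the stop signal, and score it against that same logged duration. State this as the definition of actual elapsed time.

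**Cost.** Two timestamps per run, one reworded question, one rule for empty thirds and one or two derived variables, with no added burden on participants. The small drawback is that the closing gap is only a minimum value and must be read as such.

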All equipment laid out on a table. The tissue pad is attached to the mannequin leg and surgically draped appropriately. The ultrasound probe is already in a sterile sheath, lying on the sterile field.

Instructions to subject

You are the fellow/consultant looking after Sophie. Sophie is a 2 year old girl with PIMS-TS. She is intubated and is stable on minimal ventilation and peripheral noradrenaline of 0.1mcg/kg/min. She has just been admitted to the unit. This is Sophie's bedspace, all the equipment you see is part of the simulation.

Your task is to request the admission investigations according to the sheet provided.

The nurse looking after the patient has had to step out of the bedspace to prepare their infusions and have asked you to complete your task whilst keeping an eye on the patient in the bedspace.

I am the nurse in the next bedspace, if at any point you want to make a clinical intervention please continue with the task and verbalise anything you would like me to do.

As before, when I ask you to begin, please press the foot pedal every 10 seconds, trying to be as accurate as possible. The task will last for several minutes.

Events during the task:

If this task is the first task undertaken, then the bedside monitor will display the same values throughout, aside from 1 desaturation. Heart rate: 125 bpm, blood pressure: 90/50 (65), respiratory rate: 25, oxygen saturations: 98%, end tidal CO₂: 4.5 mmHg. The oxygen saturation measure will fall to 88% for 5 seconds at 30 seconds into the task, triggering an alarm. This is to orient the participant to the monitor being part of the environment.

Normal values for age are: Heart rate: 80-140 bpm, respiration rate: 20-28 (APLS), 5th centile systolic: $65+(2 \times 2)=69$, 5th centile MAP: $50+(2 \times 2)=54$.

At 30 seconds into the task there will be a 10 second desaturation to 88% with spontaneous normalisation to 98%.

If this is the second task undertaken then values on the monitor will change during the task.

There are 2 monitor scenarios, 'A' and 'B'. Allocation between these is determined in the randomisation table (see appendix). They are identical apart from 'A' being a falling trend and 'B' a rising trend

- Scenario A
 - The oxygen saturation measure will fall to 88% for 5 seconds at 30 seconds into the task, triggering an alarm. This is to orient the participant to the monitor being part of the environment.

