 - Correct identification of no trends in other parameters - reported as proportion of participants correct
 - Accuracy of magnitude recall
 - The blood pressure either falls or rises between a systolic/diastolic (mean) of 70/48 (55) and 90/50 (65).
 - From the position of the x on the linear blood pressure scales we can derive:
 - The accuracy of the initial and final estimates compared with the actual values- reported for each task as the population mean and standard deviation of the percentage errors compared with the actual value.
 - The accuracy of the magnitude of the change, determined through comparing the difference in the estimated initial and final values compared with the actual 20mmHg systolic/ 10mmHg diastolic change for each task. The population mean and standard deviation of the percentage errors compared with the actual change will be reported for each task.
 - We hypothesised that there would be a priming effect following administration of the questionnaire, with participants more likely to attend to blood pressure trends if the questions were asked prior to the second task. We will therefore only ask the questions after the second task. We can then compare between the subgroups, split by which of the tasks was performed second to examine the impact of task type.
 - i.e the questionnaire analysis will have half the n of the overall study
- For the above we can compare subgroups using Fishers exact test.
 - By task order
 - By grade
 - By number of CVCs previously inserted

- By first 25% vs last 25% of participants

STATISTICAL CONSIDERATIONS AND DATA ANALYSIS

Sample size and statistical power

This is a pilot study and as such we do not expect it to be adequately powered to confirm hypotheses but intend that it should be hypothesis generating.

Statistical methods

The population summary statistics detailed above will be calculated using 'SPSS statistics' software with built-in min/max/mean/IQR/SD calculation.

With assumed normally distributed timing data and each participant completing 2 tasks the distributions will be compared with a paired sample t-test for; control vs administrative, control vs technical and administrative vs technical. For subgroup analysis paired or unpaired sample t-tests will be used as appropriate in each case. For the trend perception outcomes, contingency tables will be created for each subgroup and compared using Fishers exact test.

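### The scripted alarm at 30 s is in both task runs but not in the control run as described, so control-based and within-task timing comparisons may mix an alarm response with task load; the technical-versus-administrative test is protected if the response is equal

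*Combined protocol and SAP*

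**What the plan says.** The Structure table under Study procedure describes, for the first task, what the monitor shows: "The parameters do not change aside from a brief desaturation at 30 seconds into the task, to orient participants to the monitor within the task". For the second task it says: "There is a desaturation at 30 seconds as before to orient participants to the monitor within the task". The events listed for the technical task are those of the administrative task, so every task run has the alarm, whichever task comes first.

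Under Timing control, the baseline run is: "The participant sits and is asked to push a foot pedal every 10 seconds with no reference to external timekeeping". It lasts 6 minutes. No monitor, scenario or alarm is described for it.

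The primary timing outcome (Study outcomes) is the mean and SD of the intervals. Time interval analysis takes intervals from all three runs ("Intervals between pedal presses are extracted for each scenario (timing control/administrative/technical tasks"), reports each person's deviation from baseline and the proportion deviating significantly, and compares mean intervals "By time within task (split into thirds- 2 minutes each"). Under Statistical methods the runs are "compared with a paired sample t-test for; control vs administrative, control vs technical and administrative vs technical". No section excludes, flags or separately analyses the intervals around the alarm.

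In second-task runs the blood pressure also drifts, from 30 s to 4 minutes. First-task runs have no drift.

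The length of the desaturation is given in two ways under Events during the task: "The oxygen saturation measure will fall to 88% for 5 seconds at 30 seconds into the task, triggering an alarm", and then "At 30 seconds into the task there will be a 10 second desaturation to 88% with spontaneous normalisation to 98"%.

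**The concern.** The alarm is there to draw the participant's eye to the monitor. Pressing a pedal every 10 s is a concurrent attention task, so a disturbed press at about 30 s is foreseeable. If it happens, it happens in the task runs and not in the control run, and in the first third and not in the others. The analysis then has no means of separating the response to a one-off scripted event from the effect of doing the task.

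Two results could be misread. A larger SD in the task runs than at baseline could be taken as timing impaired by load. A longer mean interval in the first 2 minutes than in the last 2 could be taken as timing that changes as the task proceeds. The Outcomes and significance section links impaired time perception to the use of assistants and to policy for monitoring, so the pilot's reading of these contrasts has some weight.

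**Working it through.** **Inputs from the documents.** Run length is 6 minutes for the control and at most 6 minutes for a task; the target interval is 10 s; the alarm is at 30 s; thirds are 2 minutes each; the drift runs from 30 s to 240 s. Hence 360/10 = 36 nominal intervals per run and 120/10 = 12 per third.

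**Coverage of the thirds by scripted events.** The alarm lies in the first third only. In second-task runs the drift covers 90/120 = 75% of the first third, 100% of the second and 0% of the last. The control run as described has neither.

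**Assumptions, because the documents give no figure.** One interval is lengthened by d = 3 or 5 s; the within-run interval SD is s = 1.0, 1.5 or 2.0 s; n = 20 or 40; two-sided 5% tests. No planned n is stated. The staff pool is about 40, and the randomisation list has 20 rows per grade.

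**Effect on the mean.** The shift is d divided by the number of intervals.
- Whole run: 3/36 = 0.08 s and 5/36 = 0.14 s, which is 0.8% and 1.4% of 10 s.
- First third: 3/12 = 0.25 s and 5/12 = 0.42 s, which is 2.5% and 4.2%.

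**Effect on the SD.** The expected sample variance becomes s² + d²/36.

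| s | d = 3 s | d = 5 s |
|---|---|---|
| 1.0 | 1.12 (+12%) | 1.30 (+30%) |
| 1.5 | 1.58 (+5%) | 1.72 (+14%) |
| 2.0 | 2.06 (+3%) | 2.17 (+8%) |

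The formula depends on d², so a press that is early by d has the same effect on the SD; the shift in the mean changes sign.

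**False rejection with no load effect.** Simulation with 4,000 replicates, between-person log-SD spread 0.3, and run-to-run log-SD spread 0.2 in the control run and in the task runs. Each cell gives the rate for s = 1.0/1.5/2.0 s.

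| Comparison | 3 s delay | 5 s delay |
|---|---|---|
| SD, control vs task, n=20, all react | 33/11/7% | 92/44/18% |
| SD, control vs task, n=20, half react | 12/7/6% | 40/14/9% |
| SD, control vs task, n=40, all react | 55/17/8% | 100/72/32% |
| Mean, first vs last third, n=20, all react | 64/36/22% | 96/73/51% |
| SD, technical vs administrative, equal response | 4-6% | 4-6% |

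With no delay, every comparison rejects at about 5%. Omitting the intervals that overlap the alarm window from both runs brings control versus task back to about 5%.

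The thirds rates assume that a person's mean interval is otherwise constant through the run. If instead the SD of the paired differences is set to 1 s, a 5 s delay at n=20 gives 42% for first versus last third and 9% for the whole-run mean, control versus task.

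**The test of H_A.** The same alarm occurs at the same time in both task runs, so an equal response cancels in the paired difference. Only an unequal response matters: 5 s in one task and 2 s in the other shifts that contrast by 3/36 = 0.08 s.

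**The case against.** The strongest case against is that the contrast carrying the timing hypothesis is not exposed. H_A compares technical with administrative, and both have the alarm. A response that differs between them could itself be part of the load effect under study. This stands. A reader might infer that the alarm undermines H_A; the documents do not support that.

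Nor do the documents show that any response occurs. They give no delay, no direction and no proportion of participants reacting. A reader might infer that an alarm artefact will be reported as lost timing accuracy, but the most that can be said is that the plan could not tell the two apart. If half react, or if intervals vary by 2 s, the inflation is modest or slight.

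The control run was also never a matched environment. It is a seated baseline, and the tasks add a scenario, a monitor, verbalised interventions and the work itself. The thirds also coincide with different steps of the procedure. So the alarm is one component among several. This stands as a limit on the point, but the work is the intended contrast, whereas a one-off alarm is a nuisance that the timestamps allow one to remove.

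Finally, the study is a hypothesis-generating pilot, and the planned minimum, maximum and interquartile range could reveal an isolated long interval. Seeing it would not take it out of the mean, the SD or the paired tests.

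**Conclusion.** The point holds for control versus administrative, control versus technical, deviation from baseline and the thirds. In these, any alarm response is mixed with task load, mainly through the SD and the first-third mean. The whole-run mean moves by only 0.8-1.4% for one 3-5 s delay.

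The size rests on assumed delays and interval SDs. At n=20, false rejection on SD ranges from 5% (no delay) to 92% (everyone delayed 5 s, interval SD 1 s), with most of the intermediate settings between 6% and 44%. The technical-versus-administrative test keeps its nominal level when the alarm response is equal. This is an inexpensive improvement to the secondary reading of the timing data, not a flaw in the test of H_A.

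**What to change.** In Time interval analysis, for the control-based and thirds comparisons:

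1. Omit every interval that overlaps a fixed window around the alarm, for example 20-50 s, from all three runs, and report the all-interval result alongside.
2. Compare each third with the same third of the participant's own control run.
3. Show first-task runs, which have no pressure drift, separately from second-task runs.
4. Leave the technical-versus-administrative test on all intervals.

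The 5 s and 10 s desaturation durations must be reconciled before the window is fixed. A reader might think it safer to drop the whole first minute. That would discard 6 of 36 intervals, and half of the first third, for an event of 5 or 10 s, and it is not needed.

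The change is to analysis wording only and uses timestamps already recorded. A 30 s window costs about 3 of 36 intervals per full run (8%) and about 3 of 12 in the first third (25%), or one more when presses do not fall on the window's edges. The loss is relatively larger when a task ends before 6 minutes.
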